3.7 Visit #6: Six Months Post-Infusion

Safety and outcome assessments will be conducted in the CRU and at the HMRI 6 months from the last HB-adMSC infusion. The visit will include:

1. Interval H&P update,
2. Vital signs (Heart Rate, BP, Resp., Temp., SpO₂),
3. Blood sample for clinical labs (CBC with diff., CMP, coagulation and renal function panels) and neuro-inflammatory biomarkers,
4. A pregnancy test will be repeated for female subjects of child bearing potential (if applicable),
5. PET/DT-MRI,
6. Neurocognitive/functional outcome assessments.

The visit is expected to take about 8 hours and may require two days to complete the assessments and brain imaging.

3.8 Visits #7: One Year Post-Infusion

The one year post-infusion visit will be conducted in the CRU and is expected to take about 2 hours to complete. The visit will include:

1. Interval H&P update,
2. Physical and neurological exam,
3. Vital signs (Heart Rate, BP, Resp., Temp., SpO₂),
4. Blood sample for clinical labs (CBC with diff., CMP, coagulation and renal function panels) & neuro-inflammatory biomarkers,
5. A pregnancy test will be repeated for female subjects of child bearing potential (if applicable),
6. Chest x-ray (AP, single view),
7. Neurocognitive/functional outcome assessments.

3.9 Two Years Post-Infusion Telephone Call (End of Study)

The final safety and outcome assessment will be conducted by telephone two years after the last HB-adMSC infusion. The brief telephone interview will include an assessment of the subjects' health and adverse events or hospitalizations since the last study visit.

3.10 Participant Satisfaction Survey

Subjects or their care provider will be invited to complete an anonymous satisfaction survey in REDCap. The survey results will be used for the development of future clinical research studies requiring community based participatory research (CBPR) activities with the goal of improving research recruitment and retention.

Table 1a: Study Procedures

Study Procedures	Visit 1 Screening & Consent	Visit 2 Baseline Imaging	5 to 7 weeks for HB-AdMSC Processing	Visit 3 Inf. #1	Visit 4 Inf. #2	Visit 5 Inf. #3	Visit 6 6 Mo. Post-Inf. (+/- 21 Days)	Visit 7 1 Yr. Post-Inf. (+/- 21 Days)
Visit Location	CRU	HMRI		CRU	CRU	CRU	CRU / HMRI	CRU
Review of Medical History	X						X	X
Consent	X	X		X	X	X	X	X
Physical and Neuro Exam ¹	X	X		X	X	X	X	X
Vital Signs ²	X	X		X	X	X	X	X
Clinical Lab Evaluations ³	X			X	X	X	X	X
Research Blood Sample for TSPO Genotype	X							
Research Blood Sample for Neuroinflammatory Biomarkers	X						X	X
Neurocognitive/Functional Outcome Tests	X						X	X
Adipose Tissue Extraction ⁴ (Hope Bio. Clinical Facility)		X						
Prophylactic Lovenox ⁵				X	X	X		
Pre-Infusion Medications ⁶				X	X	X		
HB-AdMSC Infusion with 4hr. Observation ⁷				X	X	X		
Safety/Toxicity Assessments ⁸		X		X	X	X	X	X
Chest X-Ray (AP, Single View) ⁹	X							X
PET / DT-MRI Imaging ¹⁰		X					X	

1. Detailed Neuro exam optional on infusion visits based on physical exam and interval changes. **2.** Vital Signs: at baseline after consent, before and after the stem cell infusion, then q. 15min x 4, (1st hour), q. 30min. x 4 (next 2hrs.) then hourly until discharge, at follow-up visits, or more frequently if indicated.

3. CBC with diff, metabolic (CMP), coagulation and renal function panels, hCG (if applicable). **4.** Performed under Hope Biosciences IND #18388

procedures. **5.** Seven day course of prophylactic SQ Lovenox (40mg QD) beginning the day before each infusion visit. Subjects will receive a reminder telephone call the day before beginning each round of Lovenox. Lovenox will not be required for subjects already taking an anticoagulant. **6.** Benadryl

/Solumedrol (25mg for subjects <100kg or 50mg for subjects \geq 100kg.) I.V. 30 min. before infusion. **7.** Infusion given over a 1hr period (+/- 5 min.) with 14-day interval between study infusions (+/- 3 days). **8.** Assessment by telephone call 24hr. after each cell infusion and 24mo. after the last cell infusion. **9.**

Chest x-ray at baseline and end of study or more frequently if indicated. **10.** Baseline imaging will be completed within 10 days of the screening visit.

CRU- UT Clinical Research Unit

HMRI- Houston Methodist Research Institute

Hope Bio Protocol V8

Document Date: 14 JUN 2023

IRB NUMBER: HSC-MS-19-0685

IRB APPROVAL DATE: 07/31/2023

Table 1b: Study Procedures for Subjects Recruited from HSC-MS-16-0283 or HSC-MS-15-0744

Study Procedures	Visit 1 Screening & Consent	Visit 2 Baseline Imaging	5 to 7 weeks for HB-AdMSC Processing	Visit 3 Inf. #1	Visit 4 Inf. #2	Visit 5 Inf. #3	Visit 6 6 Mo. Post-Inf. (+/- 21 Days)	Visit 7 1 Yr. Post-Inf. (+/- 21 Days)
Visit Location	CRU			CRU	CRU	CRU	CRU / HMRI	CRU
Review of Medical History	X						X	X
Consent	X			X	X	X	X	X
Physical and Neuro Exam ¹	X			X	X	X	X	X
Vital Signs ²	X			X	X	X	X	X
Clinical Lab Evaluations ³	X			X	X	X	X	X
Research Blood Sample for Neuroinflammatory Biomarkers	X						X	X
Neurocognitive/Functional Outcome Tests	X						X	X
Adipose Tissue Extraction ⁴ (Hope Bio. Clinical Facility)	X							
Prophylactic Lovenox ⁵				X	X	X		
Pre-Infusion Medications ⁶				X	X	X		
HB-AdMSC Infusion with 4hr. Observation ⁷				X	X	X		
Safety/Toxicity Assessments ⁸				X	X	X	X	X
Chest X-Ray (AP, Single View) ⁹	X							X
PET / DT-MRI Imaging							X	

1. Detailed Neuro exam optional on infusion visits based on physical exam and interval changes. **2.** Vital Signs: at baseline after consent, before and after the stem cell infusion, then q. 15min x 4, (1st hour), q. 30min. x 4 (next 2hrs.) then hourly until discharge, at follow-up visits, or more frequently if indicated.

3. CBC with diff, metabolic (CMP), coagulation and renal function panels, hCG (if applicable). **4.** Performed under Hope Biosciences IND #18388 procedures. **5.** Seven day course of prophylactic SQ Lovenox (40mg QD) beginning the day before each infusion visit. Subjects will receive a reminder telephone call the day before beginning each round of Lovenox. Lovenox will not be required for subjects already taking an anticoagulant. **6.** Benadryl /Solumedrol (25mg for subjects <100kg or 50mg for subjects ≥100kg.) I.V. 30 min. before infusion. **7.** Infusion given over a 1hr period (+/- 5 min.) with 14-day interval between study infusions (+/- 3 days). **8.** Assessment by telephone call 24hr. after each cell infusion and 24mo. after the last cell infusion. **9.** Chest x-ray at baseline and end of study or more frequently if indicated.

CRU- UT Clinical Research Unit

HMRI- Houston Methodist Research Institute

4. RISKS

4.1 Respiratory Risks:

A concern exists regarding the intravenous infusion of large, adherent cells in a concentrated manner into a patient with a dysregulated systemic inflammatory response syndrome. A potential risk is amplification instead of diminution of the post-trauma pro-inflammatory response that typically manifest as exacerbation of respiratory failure or ARDS. Alternatively, the infusion could initiate a VTE event with subsequent cardiopulmonary sequelae of respiratory failure and/or right heart strain/failure. Infused cells will be evaluated for CD142 expression (cell number and intensity) and evaluated via in vitro thromboelastography for pro-coagulant activity. We plan to monitor oxygen saturation, and respiratory rate/work of breathing for the first 4 hours post-infusion. Chest x-rays will be obtained at baseline and the final study visit or more frequently if clinically indicated. We will re-examine the patient for VTE events (clinical exam, oxygen saturation) at each follow-up visit.

4.2 Hepatic Risks:

The reticuloendothelial system can sequester immature blood elements, theoretically resulting in hepatic injury. An acute elevation of the AST/ALT hepatic enzymes $> 900 \text{ U/dl}$ post-infusion will be considered an infusion related adverse event. This level is based upon the organ system scoring definitions for moderate hepatic failure and corresponds to the CTCAE v4.03 Grade 4 adverse event. It is unlikely that "end vessel" microthrombosis would occur in the liver due to the dual blood supply of the liver and the lung is the first pass organ. A comprehensive metabolic panel including AST/ALT will be drawn at each follow-up visit.

4.3 Neurologic Complications:

The patient's acute neurologic status will be evaluated at each study visit. A grade 4-5 CNS cerebrovascular ischemia event or Grade 4-5 seizure event as defined in the CTCAE v4.03 occurring within 4 hours of HB-adMSC infusion will be considered an infusion related adverse event. Other changes temporally related to HB-adMSC infusion (those events occurring within 48 to 72 hours of infusion) will be considered associated with the protocol and recorded as an adverse event.

4.4 Coagulation Cascade:

A coagulation panel will be obtained to include PT, PTT, (INR), FSP/D-Dimer, PLT thrombo-elastography, CAT, and CD142. Patients will also be monitored for the development of venous thrombo-embolic events (see pulmonary monitoring above) as well as for the development of clinical deep vein thrombosis (limb swelling, tenderness, discoloration). To minimize the risk of DVT or PE, prophylactic Lovenox SQ injections (40 mg once a day) will be given for 7 days beginning the day before each infusion visit. Lovenox will not be administered to subjects already taking an anticoagulant.

4.5 Pregnancy:

Studies to assess the reproductive and developmental toxicity of HB-adMSC's have not been conducted at this time. Women of child bearing potential (WOCBP) and men (if their sexual partners are WOCBP) must use an effective form of birth control throughout the study period. Highly effective birth control methods include sexual abstinence, surgical sterilization (hysterectomy, tubal ligation, vasectomy, etc.), hormonal contraceptives associated with inhibition of ovulation, intrauterine device, or intrauterine hormone -releasing system. Post-menopausal is defined as having no periods for at least 12 months without another medical cause.

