3.6 Visits #3 thru 5: HB-adMSC Infusions

The infusion visits will be conducted in the CRU. Subjects will receive a total of 3 infusions (2×10^8 total cells per dose) administered over a 6 week period with 14 day intervals between infusions (+/- 3 days). The volume of each infusion will be 250mL infused over a 1hr. period (+/- 5 min.) at a rate of 4-5mL per minute.

At each infusion visit, the subject will undergo the following study procedures:

1. Interval H&P update (*detailed neuro exam if indicated from interview and physical exam, current medications and recent vaccinations*),
2. Confirmation the subject started prophylactic Lovenox injections and review of the Lovenox medication logs at follow-up visits,
3. A pregnancy test will be repeated for female subjects of child bearing potential (if applicable),
4. Vital signs (Heart Rate, BP, Resp., Temp., SpO₂),
5. Insertion of a peripheral IV line,
6. Blood sample for clinical labs (CBC with diff., CMP, coagulation and renal function panels),
7. Benadryl and Solumedrol will be given as pre-meds before the infusion. The dose for both drugs will be 25mg for subjects <100kg. or 50mg for subjects $\geq 100\text{kg}$.
8. A “time out” verification of patient/consent/procedure/cell product will be performed,

9. The HB-adMSC infusion will be given by through the peripheral IV,
10. The subject will then be monitored for a minimum of 4hr.

Vital signs will be continuously monitored during the infusion and recorded at 15 minute intervals. Vital signs will be recorded at the end of the infusion and then every 15 minutes x 4 (1st hour), and then every 30 minutes x 4 (next 2 hours), and then every hour until discharge from the CRU, or more frequently if clinically indicated. A chest x-ray may be obtained if clinically indicated to assess pulmonary AE/SAE's. The subject will be contacted by telephone 24hr. after each infusion visit to determine if adverse events have occurred. Each infusion visit is expected to take around 6 hours to complete.

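### Section 4.2 counts an acute AST/ALT rise above 900 as infusion related, but no AST/ALT draw is scheduled after the cells until day 11-17 (infusions 1 and 2) or about day 162-204 (infusion 3)

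*Protocol*

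**What the plan says.** Infusional toxicity of the cell product is the primary objective (Protocol 1.1). For the liver, section 4.2 gives one numerical criterion: an acute AST/ALT elevation above 900 "post-infusion will be considered an infusion related adverse event. This level is based upon the organ system scoring definitions for moderate hepatic failure". The section ties this level to CTCAE Grade 4 and sets no time limit for *acute*. Its sampling commitment is: "A comprehensive metabolic panel including AST/ALT will be drawn at each follow-up visit".

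Section 3.6 has the three infusions "administered over a 6 week period with 14 day intervals between infusions (+/- 3 days" either way. Its numbered list for each infusion visit has, at item 6, "Blood sample for clinical labs (CBC with diff., CMP, coagulation and renal function panels"; pre-medication is item 7; and item 9 reads "The HB-adMSC infusion will be given by through the peripheral IV". After the infusion come vital signs, at least 4 hours of observation, a chest x-ray if indicated, and a telephone call at 24 hours. No further blood draw is listed.

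Tables 1a and 1b mark clinical laboratory evaluations at Visits 1, 3, 4, 5, 6 and 7. Visit 6 is 6 months (+/- 21 days) after the last infusion (section 3.7 and Table 1). The synopsis allows more frequent safety assessment when an infusion related event is suspected. Stopping rule 4 covers any Grade 4-5 event judged temporally related to the infusion.

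**The concern.** The protocol defines a hepatic event by a laboratory value and by its acute timing after infusion, yet schedules no laboratory value near that time. Respiratory risk is handled differently in section 4.1: "We plan to monitor oxygen saturation, and respiratory rate/work of breathing for the first 4 hours post-infusion".

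Two things are at stake. First, a finding of no hepatic events could be taken as evidence of acute hepatic safety when the enzymes were not routinely measured in that period. Second, stopping rule 4 could be reached by a symptom-free acute enzyme rise after infusion 3 only if someone happened to order an unscheduled sample. Such a rise gives a telephone call nothing to pick up.

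**Working it through.** **Inputs from the Protocol.** 24 subjects (8.1); three infusions, 14 +/- 3 days apart (3.6); Visit 6 at 6 months +/- 21 days after infusion 3 (3.7, Table 1a/1b); laboratory visits 1, 3, 4, 5, 6 and 7 (Table 1a/1b); the order of items in 3.6. The plan states no detection probability or power figure for this criterion, so there is none to reproduce.

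**Step 1: when the next AST/ALT falls.**
- Infusions 1 and 2: 14 - 3 = 11 and 14 + 3 = 17, so day 11-17, at the next infusion visit.
- Infusion 3: taking 6 months as 183 days, 183 - 21 = 162 and 183 + 21 = 204, so about day 162-204 (161-203 if 182 days is used).

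**Step 2: how many infusions.** 24 x 3 = 72 at most. Infusions 1 and 2 make up 24 x 2 = 48. Third infusions number 24, and 24/72 is one third. Setting aside the four subjects covered by Appendix 3, which is not in the text available: 20 x 3 = 60, of which 40 are first or second infusions and 20 are third.

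**Step 3: the infusion-day sample.** No clock time is given. That it precedes the cells is read from the list order (item 6 before item 9). If it were in fact taken afterwards, it would still be only a very early look, because "Each infusion visit is expected to take around 6 hours to complete".

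**Step 4: what a day 11-17 draw could show.** This needs a clearance rate, which the documents do not give. As an illustration, assume a single peak on day 3, then exponential decay with half-life h days, ignoring baseline. To read above 900 on day d the peak must exceed 900 x 2^((d - 3)/h). A peak of 901 leaves 901 / 2^((d - 3)/h). Values are in the unit of the criterion.

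| Assumed h | Peak needed to exceed 900 on day 11 / 14 / 17 | Left from a peak of 901 on day 11 / 14 / 17 |
|---|---|---|
| 2 days | 14,400 / 40,700 / 115,000 | 56 / 20 / 7 |
| 3 days | 5,700 / 11,400 / 22,900 | 142 / 71 / 35 |
| 5 days | 2,730 / 4,140 / 6,270 | 297 / 196 / 129 |
| 7 days | 1,990 / 2,670 / 3,600 | 408 / 303 / 225 |

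With clearance over a few days, only a peak several times the threshold would still be above 900 at the next draw. With slow clearance or continuing injury, a peak of two to four times the threshold could be confirmed. A residual rise below 900 may be visible in many of these cases.

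**Step 5: what the Visit 6 draw could show.** Under the same model, a peak of 901 on day 3 leaves less than 0.001 by day 161 for any half-life up to 7 days. The conclusion for infusion 3 hardly needs the model: a value taken more than five months later cannot establish an acute post-infusion rise.

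**The case against.** The strongest reply is that the schedule reflects a judgement about risk. Section 4.2 introduces the hazard with "The reticuloendothelial system can sequester immature blood elements, theoretically resulting in hepatic injury", and adds that microthrombosis in the liver is unlikely because of its dual blood supply and because the lung is the first-pass organ. Close respiratory monitoring with lighter hepatic monitoring would follow from that. There is also a 24-hour call after every infusion, and extra testing is permitted on suspicion. No passage plans to present an absence of hepatic events as proof of acute hepatic safety, and the SAP defines no hepatic endpoint.

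Much of this stands. It argues for a low priority and for a remedy that costs little. It does not close the gap: the protocol chose to define the event, and testing on suspicion will not find a rise without symptoms.

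A second reply is that another draw two weeks after infusion 3 would not measure an acute rise either. That is right. Such a draw shows mainly residual injury, so an early draw should be the main remedy.

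A third is that relevant text may be unseen. Appendix 3 may add draws for the first four subjects, and sections 2, 9 and 10 are not in the text available. If any of these schedules an early metabolic panel, the point falls away for the subjects it covers.

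**Conclusion.** The point holds as a gap between a stated safety criterion and the visible sampling schedule. For the 24 third infusions (of up to 72), a symptom-free acute rise cannot be seen on schedule. For the 48 first and second infusions it may have dropped below 900 by day 11-17; how often depends on clearance rates that would have to be assumed. The dates rest only on the documents, on 6 months being about 183 days, and on reading item 6 as preceding the cells.

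A reader might infer more than this, and the documents do not support it:
- *Section 4.2 contradicts the schedule.* It does not. It promises AST/ALT at follow-up visits, and Visits 6 and 7 include the panel.
- *Hepatic injury after infusions 1 and 2 would go unseen.* A residual or sustained rise may be visible at the next infusion visit.
- *The hepatic part of stopping rule 4 is unreachable.* Unscheduled testing, prompted by symptoms, can still reach it.
- *The primary safety result is biased.* Nothing in the documents indicates how often such rises occur.

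This concerns safety monitoring and the wording of the safety conclusion, not the statistical model. It is worth considering, and confidence is medium because some text is unseen.

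**What to change.** 1. Add one local-laboratory metabolic panel about 24-72 hours after each infusion to section 3.6 and Tables 1a/1b. Section 4.3 uses 48 to 72 hours for temporally related neurologic changes; 4.2 could adopt a comparable window and so define *acute*. This adds three draws per subject, 24 x 3 = 72 in total.
2. At a minimum, add one panel after infusion 3: one draw per subject, 24 in total. If it is placed at about day 14, to match the draws after infusions 1 and 2, say that it shows mainly residual injury.
3. If no early draw is added, state in 4.2 and in the safety report that acute AST/ALT was not routinely sampled, and limit the hepatic conclusion accordingly.
4. The 4.2 threshold reads U/dl in the text available, whereas exclusion 1d uses U/L; taken literally, 900 U/dl is 9,000 U/L. This may come from reading the PDF. If the source document does read U/dl, restate it in U/L.

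The cost of items 1 and 2 is one to three routine blood draws per subject. Table 1 has no visit at these times, so subjects with brain injury would need a local draw or some travel. More low-grade rises would also need review, some of them background. Items 3 and 4 change only wording.

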5. OUTCOME EVALUATIONS

5.1 MRI Evaluations:

5.1.1 MRI Acquisition and Analysis:

IRB NUMBER: HSC-MS-19-0685
IRB APPROVAL DATE: 07/31/2023

The primary goal of acquiring whole brain MRI data is twofold: 1) to quantitatively assess macro- and micro-structural properties of GM and WM regions at two time points after injury using state-of-the-art neuroimaging acquisition/analysis methods 2) to investigate macro- and micro-structural correlates of behavior in terms of cognitive performance and underlying neuropathology in a hypothesis-driven manner. To accomplish these objectives, the MRI data needs to be collected using two different, yet complementary modalities of MRI: high-resolution anatomical MRI (aMRI) and diffusion tensor imaging (DTI). The following MRI acquisition sequences will be used:

Table 2: MRI Acquisition Sequences

	FOV [mm]	Matrix	Slice thickness	No of slices (TR [msec])	No of Directions	B0	TE [ms] (TI [ms])	Coil
DTI	240 (phase: A/P)	128x192x1 , 100 % phase (reconstructed to 256) ky_dir=2 ky_dir=0	3 mm	36-40 (13,000)	32	1000	80 (N/A)	8 Ch Head (asset)
3D FSPGR	240 (phase: L/R)	224x352x1 75%phase (reconstructed to 512)	1 mm	128 (9.5)	N/A	N/A	3.9 (450)	
B0 fieldmap FSPGR		256x256x2 (nex) Also, set rhccctrl to 3	1 mm	Same as Anatomical scans (50, angle 30 degrees, BW 16kHz)	N/A	N/A	10 ms and 15 ms	
BOLD	220 (phase: A/P)	64x64x1 (epiRT)	3mm	30 (cover whole head)	N/A	N/A	35	

The details of analysis of the imaging data go beyond the space limitations of the synopsis section but are described in more detail in the Investigator Brochure.

5.1.2 [¹¹C]ER-176 PET Imaging:

Upon meeting inclusion/exclusion criteria, subjects will be scheduled for a PET/DT-MRI scan. All female subjects will be given a urine pregnancy test prior to each PET scan. The results of this test will be kept as part of their confidential research record. A positive screen will disqualify them from participation in the study. Following their PET/DT-MRI scan, subjects will be contacted within 24-48 hours by a licensed study clinician to ascertain the presence/absence of unforeseen complications. Clinical complications will trigger an appropriate medical intervention and/or referral.

For the PET scan we will be using the tracer/label [¹¹C]ER-176. This tracer binds to proteins in the brain that we believe are involved in regulating the neuroinflammatory response to injury. PET scans may include an affective challenge presented to the patient during the PET scanning period (e.g. induction of mood, affective pain, etc.). Subjects will then be asked to lay quietly without movement on a cot with their head located within the PET "camera". To permit tracer injection and withdrawal of blood samples, an IV will be inserted into a vein in both arms. [¹¹C]ER-176 will be injected into subjects' vein during PET scanning by qualified and hospital approved/designated personnel. At various points throughout the scan, subjects' blood pressure, heart rate, breathing rate and blood oxygen saturation may be recorded. If any of the MRI or PET data is compromised, subjects may be asked to repeat either the whole procedure or the portion compromised. However, subjects have no obligation to honor this request. Subjects will be compensated for their time.

5.1.3 Post PET Scanning:

Immediately following completion of PET scanning, subjects will remain in the PET suite and be observed by staff qualified to determine the presence of adverse effects/sequelae to the PET scanning procedure. Subjects will meet with study personnel (office, phone, video chat, etc.) to complete neuro/psychometric measures and to determine the presence of unforeseen/untoward study complications.

5.2 Neurocognitive and Functional Outcomes Evaluations:

Neuropsychological outcome testing will be overseen by [name]. The battery includes core NIH common data elements for moderate/severe TBI outcomes, recommended measures from the NIH toolbox, and TBI Quality of Life patient-reported outcomes.

Table 3:

Hope Bio Study – Testing Timeline		
Baseline - Visit 1	6 Month - Visit 6	12 Month - Visit 7
Screening	6mo post-infusion	12mo post-infusion
Caregiver Interview		
Glasgow Outcome Scale - Extended (GOS-E)		
Self-Reports		
Galveston Orientation and Amnesia Test (GOAT)		
TBI Quality of Life Questionnaires (TBI-QOL SF)		
Brief Symptom Inventory 18 (BSI 18)		
Neuropsychological Assessments		
NIH Toolbox – Motor: 9-hole Pegboard Dexterity Test		
NIH Toolbox – Cognition: Flanker Inhibitory Control and Attention Test		
NIH Toolbox – Cognition: List Sorting Working Memory Test		
NIH Toolbox – Cognition: Picture Vocabulary Test (Baseline and 12M)		
NIH Toolbox – Cognition: Dimensional Change Card Sort Test		
NIH Toolbox – Cognition: Pattern Comparison Processing Speed Test		
Rey Auditory Verbal Learning Test (RAVLT)		
D-KEFS: Verbal Fluency (VF)		
Wechsler Adult Intelligence Scale - IV: Coding (WAIS IV – CD)		
Wechsler Adult Intelligence Scale – IV: Symbol Search (WAIS IV – SS)		

5.3 Cytokines and Pro/Anti-Inflammatory Marker Evaluation:

Plasma cytokines, IL-1 α , IL-4, TNF α , IL-6, IL-10 and albumin will be measured via a bead-based, flow cytometric ELISA for the cytokines, and BCG immunochemical analysis for albumin concentration. Samples will be obtained at the baseline imaging visit #2, and at the 6 and 12 month follow-up visits. This approach is based on findings that cytokine markers may be a useful biological effect marker for Phase 2 and 3 trials.

